### Research Objectives/Background

1. Include primary, secondary, and exploratory objectives.  
**Primary goal: to evaluate whether allowing showering after a certain number of days post breast reconstruction has an effect on the infection rate**  
**Secondary goal: to evaluate whether allowing showering after a certain number of days post breast reconstruction has an effect on the quality of life of patients**
2. Include background and rationale for initiating the study. Includes pre-clinical and clinical data, current experiences with procedures, drug, or device, and any other relevant information to justify the research.  
**Currently, there is a lack of consensus on best practices regarding showering with drains in place following first stage breast reconstruction. There is anecdotal concern for an increased risk of Surgical Site Infection (SSI), but the current literature to support this is lacking. There is also some evidence that showering with drain tubes in place has no increase risk of infection. It is not known whether showering with drain tubes decreases the risk of SSI. Surgical drains can remain in place upwards of two to three weeks in the postoperative period. The recommendation not to shower until drain removal can present a significant challenge for patients resulting in distress and decreased quality of life. Our study will assess the infection rates in patients allowed to shower at 48 hours postoperatively compared to those not showering until drains are removed. Our hypothesis is that this study will reveal no difference in the rates of SSI and improved quality of life in patients who are allowed to shower with drain tubes in place.**

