### Study Procedures/ Design/Treatment Plan

1. Include study procedures/design/plan; include the sequence and timing of study procedures (distinguish research procedures from those that are part of routine care). Include study duration and number of study visits required.  
**Study will last 90 days. Patient's will be admitted to the hospital following surgery if the reconstruction takes place immediately following mastectomy. If the reconstruction does not occur at the same time as mastectomy, patients are not admitted. This is part of our routine care. Regardless, they will be evaluated on post operative day one. Following the initial post operative day one visit, patient's will be evaluated on a weekly basis for 90 days. Vitals will be taken at the visits, and routine physical examination (including evaluation for surgical site infection) will be performed. Patient reported outcomes will be obtained at these visits as well. We will also ask patients if they have been showering or not and if so how often. This will be documented. For example: patient evaluations will be as follows:**
  - One-month preoperative visit
  - Day of surgery
  - Post Operative Day one evaluation (In the hospital or clinic)
  - Clinic Visit 1: One week after surgery
  - Clinic Visit 2: Two weeks after surgery

**These visits will not differ from our routine care. At the conclusion of 90 days patients will receive a survey asking if drain care and the ability or inability to shower with drain tubes in place adversely affected their quality of life.**

2. Blinding, including justification for blinding or not blinding the trial. Describe unblinding procedures.  
**The study will not be blinded. Participants will be randomly assigned to treatment arm. Researchers and patients will know which arm they are assigned to.**
3. Justification of why participants will not receive routine care or will have current therapy stopped.  
**The goal of the study is to determine if there an effect on infection rate with allowing patients to begin showering 48 hours after surgery rather than waiting to shower until drains are removed. There is no definitive literature on this, and the care of surgical drains is ultimately decided by the surgeon. There is currently no defined standard of care regarding showering with surgical drains in place.**

4. Definition of treatment failure or participant removal criteria.  

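### The 90-day survey asks patients whether their own arm's showering rule harmed them, so a difference between arms on it cannot by itself show an effect on quality of life

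*Protocol*

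**What the plan says.** In the Protocol, Research Objectives/Background, the secondary goal is whether permitted showering "has an effect on the quality of life of patients". The hypothesis in the same section is "improved quality of life in patients who are allowed to shower with drain tubes in place".

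Study Procedures/ Design/Treatment Plan, item 1, describes the survey: "At the conclusion of 90 days patients will receive a survey" on whether drain care and "the ability or inability to shower with drain tubes in place adversely affected their quality of life". Only the survey's content is described. Its wording, response scale and recall period are not shown.

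The same item says of the weekly visits: "Patient reported outcomes will be obtained at these visits as well". It names no instrument for these outcomes and does not link them to the secondary goal.

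Item 2 of that section states: "Researchers and patients will know which arm they are assigned to". Number of Subjects gives 50 patients per arm.

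**The concern.** A randomised comparison needs the same quantity measured in both arms. Here the subject of the question changes with the arm. While drains are in, a control patient has only a ban to judge, and a patient in the showering arm has only a permission.

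The question also asks for attribution (did this rule harm you?) rather than for a level (how good was your quality of life?). Two patients with the same quality of life can answer differently because only one of them was forbidden something.

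Finally, it runs in one direction. It can record harm, but not the improvement that the hypothesis predicts.

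At stake is the secondary conclusion. A higher proportion of complaints among controls could be reported as better quality of life with showering, when it may show only that some people told not to shower blamed that rule. No later analysis can recover a common outcome from these answers, so this is not a detail that can be left to an analysis plan.

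The joining of drain care with showering and the day-90 timing are separate matters. This problem would remain if the showering part stood alone and were asked while drains were in.

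**Working it through.** **1. Goal and item side by side**

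| | Goal and hypothesis | Survey as described |
|---|---|---|
| Quantity | Effect on quality of life | Whether a rule, with drain care, did harm |
| What is rated in the showering arm | Quality of life | Ability to shower |
| What is rated in the control arm | Quality of life | Inability to shower |
| Direction | Improvement expected | Harm only |
| Respondent | – | Knows the assigned arm |

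The two columns match only if answers about attributed harm track quality of life equally well in both arms. Nothing in the protocol supports that.

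**2. How large could the artefact be?** The protocol gives no response rates, significance level or test for this item, so it has no figure of its own to reproduce. What follows is illustration under assumptions.

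Inputs: 50 per arm (Number of Subjects). Assumed: all patients respond, true quality of life is equal in the two arms, and the proportions answering yes are compared by a two-sided Fisher exact test at 5%.

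Formula: P(significant) = Σ over a, b of Bin(a; 50, p_C) × Bin(b; 50, p_S) × I[Fisher p ≤ 0.05]. Here a and b are the numbers answering yes among controls and in the showering arm, and p_C and p_S are the corresponding probabilities.

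*Showering-only item:*

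| p_C | p_S | P(significant) |
|---|---|---|
| 20% | 5% | 0.508 |
| 30% | 10% | 0.640 |
| 20% | 2% | 0.779 |
| 30% | 5% | 0.899 |
| 40% | 5% | 0.992 |

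*Item that also covers drain care, as described.* Let a share d of both arms say yes because of drain care, and let a further independent share s of controls blame the ban. Then p_S = d and p_C = 1 − (1 − d)(1 − s).

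| d | s | p_C | P(significant) |
|---|---|---|---|
| 30% | 20% | 1 − 0.70 × 0.80 = 44% | 0.24 |
| 60% | 20% | 1 − 0.40 × 0.80 = 68% | 0.09 |
| 30% | 40% | 1 − 0.70 × 0.60 = 58% | 0.77 |
| 60% | 40% | 1 − 0.40 × 0.60 = 76% | 0.33 |

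*No attribution gap (s = 0):* p_C = p_S, and the test stays within its nominal 5%. There is no excess.

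**3. What a neutral rating could detect.** For a two-sample comparison of means with 50 per arm, two-sided 5% and 80% power, the normal approximation gives d = (1.96 + 0.84) × √(2/50) = 2.80 × 0.20 = 0.56. The t-test calculation gives 0.566, so about 0.57 standard deviations.

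**The case against.** The strongest reply has four parts.

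- **The protocol only paraphrases the survey.** Ability or inability may be shorthand covering both arms, and the real questions may be better. This stands as a limit: the point concerns the content the protocol commits to, not an instrument anyone here has seen.
- **The weekly patient-reported outcomes may already contain a common quality-of-life scale, and those visits span the drain period.** A reader might infer that the survey is the only possible evidence on quality of life, and the document does not support that. Nor does it say that these outcomes cover quality of life or serve the secondary goal. They could supply the cure, but they are not stated to be it.
- **Bias is not certain.** A reader might infer that a difference favouring showering is built in. It is not: a control patient untroubled by the ban can answer no, and the protocol allows controls sponge baths to ease discomfort. The protocol also says that infection risk with showering may be higher, lower or the same, so a patient in the showering arm could report worry or burden. This stands.
- **The probabilities are partly circular.** They assume unequal answers and equal quality of life, whereas complaints from controls could reflect a real effect. That is fair, and the protocol states no between-arm test on this item. But it also shows why the item fails: it cannot tell a real loss of quality of life from attribution alone.

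A reader might also infer that this item would be used to justify changing practice. Anticipated Benefits mentions the ability to change practice to improve quality of life, but does not say that this survey would be the basis.

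**Conclusion.** The point holds in a limited form. As described, the 90-day survey measures attributed harm with a referent that differs by arm, in patients who know their arm. By itself it cannot establish the secondary goal or the hypothesised improvement in quality of life.

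The likely direction of bias favours showering, but neither its presence nor its size can be fixed from the document. With 50 per arm and equal true quality of life, the chance of a significant difference is:

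- within the nominal 5% if there is no attribution gap;
- about 9% to 24% if 20% of controls blame the ban amid 60% or 30% shared drain-care complaints;
- 51% to 99% for a showering-only item at 20% v 5% to 40% v 5%.

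All of these response rates are assumptions, as are the Fisher test and full response. The argument about what the item measures does not depend on them. The matter concerns a secondary objective and should be corrected; it does not touch the infection comparison.

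**What to change.** In Study Procedures/ Design/Treatment Plan, item 1:

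1. State that the arms are compared on one quality-of-life rating, worded identically for everyone, for a stated period, with no mention of showering, drains or assigned arm. Place it before any question on showering.
2. The rating may be taken through the patient-reported outcomes already collected at the weekly visits. If so, say that they include it and that it serves the secondary goal. Those visits cover the weeks when the two showering rules differ; the protocol says "Surgical drains can remain in place upwards of two to three weeks in the postoperative period".
3. Keep the attribution question as description within each arm, and state that it does not support a claim of improved quality of life.

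The cost is one added question and an edit to the survey text. Visits, treatment and sample size do not change. The drawback is that a neutral rating will probably show a smaller difference: with 50 per arm, 80% power needs a standardised difference of about 0.57, so a modest true effect could be missed.

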### Number of Subjects

1. Include anticipated enrollment number in this study. Include a break-down in numbers if there is more than one subject population.  
**Our goal is to achieve an  $n$  of 100 with 50 patients allocated to the experimental arm (showering at 48hrs) and 50 allocated to the control (current standard of care).**
2. Include statistical analysis or other justification for the number of subjects enrolled.  
**An  $n$  of 100 provides us with adequate power for a statistically significant difference between subject arms to be detected if one is present.**

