**Removal criteria: failure to shower within 48 hours (experimental arm) or showering before surgical drain removal (Control group). Other removal criteria will be participants that have violated the post operative instructions in any way.**
5. Description of what happens to participants receiving therapy when study ends or if participation in the study ends prematurely.  
**At the end of the study or if patients choose to withdraw prematurely from the study, patients will continue to follow up at designated intervals for general postoperative monitoring.**
6. Include sub-studies or banking information (correlative/special studies)  

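### Randomised patients are removed for not keeping to their arm, with no provision to keep their outcomes, and the 48-hour removal trigger conflicts with the assigned schedule

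*Protocol*

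**What the plan says.** All references are to the Protocol.

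- **Removal (Study Procedures/Design/Treatment Plan, item 4).** The arm-specific grounds are "Removal criteria: failure to shower within 48 hours (experimental arm) or showering before surgical drain removal (Control group". A general ground follows: "Other removal criteria will be participants that have violated the post operative instructions in any way".
- **After leaving the study (same section, item 5).** The text covers the end of the study and the patient's own choice to leave: "if patients choose to withdraw prematurely from the study, patients will continue to follow up at designated intervals for general postoperative monitoring". It does not mention patients whom the investigators remove.
- **Question (Research Objectives/Background).** The primary goal is "to evaluate whether allowing showering after a certain number of days post breast reconstruction has an effect on the infection rate". The secondary goal asks the same of quality of life. The comparison is of "patients allowed to shower at 48 hours postoperatively compared to those not showering until drains are removed", and the stated expectation is "Our hypothesis is that this study will reveal no difference in the rates of SSI".
- **Timing of the experimental arm.** Number of Subjects has "50 patients allocated to the experimental arm (showering at 48hrs". Item 3 of Study Procedures has "allowing patients to begin showering 48 hours after surgery rather than waiting to shower until drains are removed". The Costs section places showering later than the 48-hour point.
- **Conduct (Study Procedures, items 1 and 2).** The trial is unblinded. Patients are asked at visits whether and how often they shower. A survey on how drain care and the shower restriction affected quality of life is given once 90 days are complete.

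**The concern.** Randomisation makes the arms comparable only as randomised. Here the set of patients who remain depends on later behaviour, and the behaviour that counts differs: omitting an act in one arm, committing it in the other. The catch-all ground leaves further removals to the judgement of staff who know the assignment.

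The Protocol itself suggests that removal may be related to outcome:

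- Patients are told not to soak in a bath, as a measure against infection. One who does has broken an instruction and can be removed.
- The background reports anecdotal concern that showering with drains raises SSI risk. Controls with exactly that exposure are removed.
- The background says the restriction can cause distress. The controls most troubled by it may be the likeliest to break it, and would be gone before the day-90 survey.

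These links are inferences; their strength and direction are unknown.

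The objective is also at stake. Both goals concern permission to shower. A patient who is permitted to shower and does not has, on that wording, received the assigned policy, yet meets the removal criterion. If outcomes stop at removal, neither an as-assigned nor a full adherence-based analysis can be built later, and a statistical analysis plan (SAP) cannot supply a survey that was never given.

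**Working it through.** **1. The timing passages side by side**

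| Place | Showering in the experimental arm |
|---|---|
| Number of Subjects, item 1 | at 48 hours |
| Study Procedures, item 3 | begins 48 hours after surgery |
| Costs, item 1 | later than 48 hours |
| Study Procedures, item 4 | removed if not done inside 48 hours |

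Counted from surgery, the first and second rows meet the fourth only at the 48-hour point itself; the third cannot meet it. So up to all 50 experimental patients could follow the schedule in item 3 or Costs and still qualify for removal. If item 4 counts from the moment of permission the conflict disappears, but the text does not say so.

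**2. Can the trigger be observed?** The visits listed around this time are postoperative day one and one week. The showering question, as described, covers whether and how often. Time of first shower is not a stated data item, so for patients no longer in hospital the 48-hour test would rest on later recall.

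**3. Size of the possible bias.** The only relevant figure in the Protocol is 50 per arm. It gives no SSI rate, non-adherence rate or allowance for removals, so there is no figure of its own to reproduce. The rates below are assumptions.

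Let p be the true SSI risk (the same in both arms), q the fraction removed, and RR the risk in removed relative to retained patients. Then

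retained risk = p / (1 − q + q·RR)

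*One arm only, p = 10%:*

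| q | RR | Retained risk | Shift (points) |
|---|---|---|---|
| 0.1 | 1.5 | 0.10/1.05 = 9.52% | 0.48 |
| 0.2 | 2 | 0.10/1.20 = 8.33% | 1.67 |
| 0.3 | 3 | 0.10/1.60 = 6.25% | 3.75 |

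The first and last rows become 0.24 and 1.87 points at p = 5%, and 0.95 and 7.50 points at p = 20%. The sign depends on which arm loses patients. It also reverses if those removed have the lower risk: with 20% removed at a 5% risk, the retained risk is (0.10 − 0.2 × 0.05)/0.8 = 11.25%.

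*Both arms, p = 10%, q = 0.2:*

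- RR 2 in each: 8.33% − 8.33% = 0.
- RR 1.5 in one and 3 in the other: 0.10/1.10 − 0.10/1.40 = 9.09% − 7.14% = 1.95 points, with the sign set by which arm is which.

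**4. Against sampling error.** The 95% half-width for a difference, with 10% in each arm, is 1.96·√(2 × 0.09/n):

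- n = 50: 11.76 points.
- n = 40 (20% lost per arm): 13.15 points.

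The largest 10% shift is 3.75/11.76 = 0.32, about a third of the full-sample half-width.

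**5. What as-assigned analysis costs.** Assume true risks of 20% and 10% by actual behaviour, with a fraction c crossing over in each arm. The observed difference is

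[(1 − c)·0.20 + c·0.10] − [(1 − c)·0.10 + c·0.20] = 0.10·(1 − 2c)

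For c = 0.1, 0.2 and 0.3 this is 8, 6 and 4 points.

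**The case against.** The strongest reply is that removal from the study is not exclusion from analysis. Item 4 names no analysis set, and analysis sets commonly belong in an SAP, which is not at hand. That is right as to the literal text. It does not answer the gap in collection, which an SAP cannot repair.

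Next, SSI may survive anyway. The visits are described as routine care, run weekly to 90 days and include examination for infection. Item 5 answers a prompt about any premature end of participation. This has force: loss of the primary outcome is not established. But item 5 literally covers only study end and voluntary withdrawal, and promises clinical care, not outcome data. The day-90 survey is the part most clearly exposed.

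Third, the Protocol also describes the intervention as showering itself (Number of Subjects, Costs, and the instruction under Potential Risks), so not showering may be genuine non-adherence. That stands; the document wavers between policy and behaviour. Non-adherence is still no reason to stop measuring a randomised patient.

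Fourth, the visit list is given as an example, and some patients are admitted, so some first showers might be seen in hospital. This narrows the recall point without removing it.

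Last, the bias figures depend on assumed inputs, and the shift is zero when removal is balanced or unrelated to outcome. That is accepted.

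**Conclusion.** The concern holds and should be fixed before the trial relies on this rule. Three things follow from the text alone: arm-specific and open-ended removal after randomisation, no provision for the outcomes of those removed, and a 48-hour trigger at odds with the assigned schedule.

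That the SSI and quality-of-life comparisons would be biased is conditional: removed patients must be left out of the analysis, or their outcomes never collected, and removal must be related to outcome differently in the two arms. The direction is unknown. With removal from one arm only, within the assumed ranges, the shift in the SSI difference is about 0.5 to 3.8 points at 10% true SSI, 0.2 to 1.9 at 5%, and 1.0 to 7.5 at 20%. At 10% that is smaller than sampling error with 50 per arm. But it is systematic, and neither a larger sample nor a later SAP would remove it.

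**What to change.** 1. In item 4, drop non-adherence and breach of instructions as grounds for removal from the study, and record them as deviations.
2. In item 5, state that SSI to day 90 and the day-90 survey are collected for every randomised patient unless consent is withdrawn.
3. Make the comparison by assigned arm primary for SSI and quality of life, here or in the SAP. Pre-specify a per-protocol analysis to be reported beside it: crossover pulls the as-assigned result toward the trial's own hypothesis of no difference in SSI, so a null result needs both. How prominent the second should be is open to judgement.
4. Add date and time of first shower and date of drain removal to the showering question already asked.
5. Reconcile the 48-hour wording across Number of Subjects, Study Procedures items 3 and 4, and Costs. Which timing is meant is for the investigators to decide.

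The administrative cost is protocol wording, two data items, and giving the survey to non-adherers. SSI capture adds little, since the visits are described as routine. The real cost is dilution, as shown in the working (a 10-point difference falls to 6 with 20% crossover per arm), and the quality-of-life contrast may shrink too.

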**Data must be kept for seven years after the study has been completed.**

### Potential Risks/Adverse Events

1. Describe reasonably foreseeable risks or discomforts to the subjects and steps to minimize risks.  
**The study involves minimal risks and steps will be taken to mitigate these risks. Risks include: soft tissue infection, breast implant infection, decreased quality of life, breach of confidentiality. Infection risk may be higher, lower, or the same in those who allowed to shower with drains in place compared to those not allowed to shower. There is a lack of literature to support increased risk of infection with showering with JP drains in place. Timing of showering is ultimately surgeon dependent. Regardless, this risk will be mitigated by continuing with sterile surgical technique with proper prepping and draping of the patient as well as sterile placement of drain tubes intra-operatively. Patient's will also be instructed to not soak in water, such as in a bath tub. Rather, they will be instructed to shower and let water run over the drain tube sites. Patients will be immediately treated if there any signs of infection. In terms of decreased quality of life, patients who will not be allowed to shower until drain tubes are removed will be allowed to sponge bath to help mitigate any discomfort. The final risk is possible breach of confidentiality. These risks will be minimized by de-identification of data collected on a separate file, a link between randomly assigned number and identifiable data will be listed. All data collected will be secured on a password protected excel spreadsheet. No persons outside those listed. Accidental removal of a surgical drain is not increased by this study. It is part of our routine care to suture the drain tubes to the skin. Accidental dislodgement of drains is an extremely rare event and is part of the normal post operative surgical risks.**
2. Describe any stopping rules.  
**We would immediately withdraw patients per their request. We would also stop the study all together if there was a clear statistical benefit in one of the study arms.**
3. Include the plan for reporting unanticipated problems or deviations. This plan must include a five-day reporting requirement to the IRB once becoming aware of an event.  

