**No compensation will be provided. Patients will be recruited for this study on a volunteer basis.**

### **Costs**

1. Detail costs of study procedures, drugs, biologics, or devices and identify who will cover the cost.  
**There is no attributed cost for study procedures. We will be implementing two treatment arms: showering after 48 hours post operative with JP drains in place vs showering after JP drain removal. Survey will be voluntary**

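### The experimental-arm removal rule makes 48 hours a deadline for showering, while the arm itself makes 48 hours the earliest time, so patients who follow the arm can be removed

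*Protocol*

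**What the plan says.** The protocol's Study Procedures/ Design/Treatment Plan, item 4, sets the removal criteria: "Removal criteria: failure to shower within 48 hours (experimental arm) or showering before surgical drain removal (Control group". It does not say when the 48 hours start. A second sentence in the item removes any participant who departs from the post-operative instructions.

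The experimental arm is described in four other places:

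- Study Procedures, item 3, gives the aim as "allowing patients to begin showering 48 hours after surgery rather than waiting to shower until drains are removed".
- Costs, item 1, describes the two arms as "showering after 48 hours post operative with JP drains in place vs showering after JP drain removal".
- Research Objectives/Background, item 2, and Number of Subjects, item 1, place showering at 48 hours. The latter plans 50 patients per arm.

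Three further statements bear on how the rule would work:

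- The trial is open: "Researchers and patients will know which arm they are assigned to" (Study Procedures, item 2).
- The background says of drain duration: "Surgical drains can remain in place upwards of two to three weeks in the postoperative period".
- On follow-up, item 5 says that "patients will continue to follow up at designated intervals for general postoperative monitoring", but this is written for the end of the study and for patients who choose to withdraw.

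**The concern.** The removal rule and the arm definition use the same figure in opposite directions: one as a latest time, the other as an earliest time. There is also a difference in kind. The background and item 3 describe a permission to shower; the removal rule turns it into an obligation with a deadline.

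This matters because the rule decides who stays in the trial after randomisation. Applied as written, it removes experimental patients who did what the arm asks. Not applied as written, it leaves staff who know the allocation to choose what it means. The control criterion, showering before the drains come out, needs no such interpretation, so the ambiguity in the timing rule lies in one arm only. If patients who delay their first shower differ in infection risk, for instance because of pain or worry about the wound, removing them would distort the comparison of infection rates. That last step is reasoning; the protocol gives no data on it.

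**Working it through.** No sample-size or power figure is involved. The check compares the passages directly.

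Let *t* be the hours from surgery to first shower in the experimental arm.

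**Arm as defined.** Study Procedures item 3 gives *t* ≥ 48. Costs item 1 gives *t* > 48. The wording in the background and in Number of Subjects places showering at 48 hours, which is only a weak conflict with the removal rule, since *t* = 48 satisfies both.

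**Start of the clock.** The removal rule gives none. The background, item 3 and the Costs section count their 48 hours from surgery. No section offers another start.

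**Latest first shower that avoids removal, under three readings:**

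| Reading | Written in the protocol? | Latest *t* | Window after 48 h |
|---|---|---|---|
| R1: 48 h counted from surgery | The only clock given | 48 h | 48 − 48 = 0 h |
| R2: 48 h counted from when showering is allowed | No | 48 + 48 = 96 h | 96 − 48 = 48 h |
| R3: must start before drain removal | No | 14 × 24 = 336 h to 21 × 24 = 504 h | 336 − 48 = 288 h to 504 − 48 = 456 h |

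R3 uses the two to three weeks given in the background. That wording is not a firm ceiling, so the range is illustrative.

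**Overlap under R1.** The rule retains *t* ≤ 48. Against item 3 the two sets share the single point *t* = 48. Against the Costs wording they share nothing.

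**Two example patients, drains still in place:**

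| First shower | R1 | R2 | R3 |
|---|---|---|---|
| 72 h | removed | kept | kept |
| 120 h | removed | removed | kept |

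**Early showering.** The safety section's instruction, "Rather, they will be instructed to shower and let water run over the drain tube sites", sets no earliest time. It therefore cannot be said that a patient who showers before 48 hours would also be removed.

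**Number affected.** Under R1 the number removed is 50 × (share with *t* > 48). The share is unknown because no distribution of first-shower times is given. As a scale only, 0.10 × 50 = 5 patients for each 10% of the arm.

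**Can the rule be checked from the planned data?** The listed post-operative evaluations are on day one (about 24 h) and at one week (7 × 24 = 168 h), then weekly. Patients are asked whether and how often they shower, but not when they first did. First showers at 48, 72, 96 and 120 hours all fall between the same two evaluations and cannot be told apart from that question.

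**The case against.** The strongest reply is that this is an undefined clock rather than a contradiction. The conflict appears only once the reader supplies surgery as the start, and the wording in Number of Subjects meets the rule at exactly 48 hours. A window of zero hours for an adherent patient also looks like a drafting slip that nobody would enforce, and the data described could hardly support enforcing it. It is probably right that the literal effect was not intended. That does not repair the rule: surgery is the only clock in the document, and the two milder readings disagree with each other at 120 hours, so knowing that the literal reading was unintended does not tell staff which one to use.

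A second point is that the catch-all removal sentence for breaches of post-operative instructions applies to both arms and is just as discretionary. This stands. Correcting the 48-hour clause alone leaves that discretion in place, which is a reason to replace removal with recorded deviations in both arms.

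A third is that analysis sets may be covered in a statistical analysis plan that is not at hand. That is fair, and the absence of an analysis population is not the point here. Removal criteria are fixed in the protocol and applied in the clinic; an analysis plan would not correct their wording.

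Finally, no count of affected patients can be given. That is true, and it limits how strongly the point can be put.

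**Conclusion.** The concern holds and should be fixed. With the clock started at surgery, the removal rule conflicts with the arm as defined in Study Procedures item 3 and in the Costs section: a patient who first showers at 72 hours with drains in place follows the arm and meets a removal criterion. The only assumption is that the unstated clock starts at surgery, as it does wherever the protocol gives a start. Without that assumption the limit could lie anywhere from 48 hours to drain removal, and staff who know the allocation would have to choose, in the experimental arm only.

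The rule applies to all 50 planned experimental patients; how many would be removed cannot be derived from the document. The protocol also does not say whether patients removed under this rule remain in study follow-up, since its follow-up sentence addresses only study end and voluntary withdrawal.

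**What to change.** Reword the experimental-arm criterion so that non-adherence means not starting to shower within a stated window that opens 48 hours after surgery, while drains are in place. The investigator should set the length; a 48-hour window, for example, would close at 96 hours. If patients are to be told not to shower before 48 hours, say so in the instructions and count earlier showering as non-adherence too.

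Record departures in either arm, including breaches of the post-operative instructions, as deviations instead of grounds for removal. Keep these patients in the 90-day follow-up and analyse them in the assigned arm. Add the date of first shower to the showering question already asked at visits.

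The cost is a rewritten removal item and one small data item. Replacing removal with retention is a change of stated policy as well as of wording, but it needs no extra visits: of the existing schedule the protocol says "These visits will not differ from our routine care".
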